1. OBJECTIVES

1.1 Primary Objectives

- 1.1.1** To conduct a phase I study to evaluate the safety and tolerability of this combination of chemotherapy agents.
- 1.1.2** To determine the response of children with recurrent or refractory central nervous system tumors with this combination of chemotherapy agents.

1.2 Secondary Objectives

- 1.2.1** To compare the response and toxicity with historical controls in prior published studies of patients with the same disease.
- 1.2.2** To estimate the 2- and 5-year survival with children treated with this regimen.
- 1.2.3** To provide safety and efficacy data to recommend further larger studies.

2. PATIENT SELECTION

2.1 Inclusion Criteria

- 2.1.1** Patients must have histologically confirmed (exception: diffuse intrinsic pontine glioma or optic pathway tumor) central nervous system malignancy for which standard curative measures do not exist or are no longer effective (i.e. patient must have received prior standard therapy in order to be considered eligible).
- 2.1.2** Patients must have measurable disease (see section 10.1.2 for definition of measurable disease).
- 2.1.3** Prior therapy restrictions:
 - Patient may not have received vorinostat and lenalidomide in combination.
 - At least 3 weeks since prior chemotherapy.
 - At least 6 weeks from last nitrosurea.
 - At least 6 weeks from autologous transplant.
 - At least 3 months from bone marrow donor transplant.
 - At least 3 weeks from focal radiation.
 - At least 6 weeks from craniospinal radiation.
 - Must have not received growth factors within 1 week of study entry.
 - Must be on a stable or decreasing dose of steroids for 1 week prior.
 - Must not be receiving any chemo, biologic, or radiation therapy.
 - Must not be receiving enzyme inducing anticonvulsants or valproic acid.

- Must not be receiving pro-thrombotic agents

2.1.4 ≥ 1 Age (in years) < 21

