3.1.7 Pregnancy and breast feeding

The effects of vorinostat and lenalidomide on the developing human fetus are unknown. For this reason and because agents used in this trial are known to be teratogenic, women of child-bearing potential must commit to complete abstinence or use TWO methods of birth control (one highly effective (i.e. IUD, birth control pills, injections, implants, tubal ligation, partner's vasectomy), and one additional method (i.e. male condom, diaphragm, cervical cap) for the duration of study participation and at least 28 days after completion. Females of childbearing potential must agree to ongoing pregnancy testing and counseling every 28 days about pregnancy precautions. If a female has not had a menstrual period in the preceding 24 consecutive months or has had a hysterectomy, the two methods of birth control requirement does not apply. Should a woman become pregnant or suspect she is pregnant while she or her partner is participating in this study, she should inform her treating physician immediately. Men treated or enrolled on this protocol must agree to use condoms for the duration of study participation, and 28 days after completion.

3.1.8 Patient or guardian ability to understand and provide written informed consent.

3.1.9 Must be able to swallow lenalidomide capsules.

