2.2 Exclusion Criteria

2.2.1 Patient has not recovered from acute toxic effects of all prior therapies.

2.2.2 Patients who are receiving any other investigational agents.

2.2.3 History of allergic reactions attributed to compounds of similar chemical or biologic composition to vorinostat or lenalidomide.

- 2.2.4 Uncontrolled intercurrent illness including, but not limited to, ongoing or active infection, dyspnea at rest, symptomatic congestive heart failure, history of thromboembolism unrelated to central line, patients with known predisposition syndrome for thromboembolism, patients receiving anticoagulation therapy, unstable angina pectoris, cardiac arrhythmia, patients receiving enzyme inducing anticonvulsants, patients receiving valproic acid, patients receiving antiplatelet agents (aspirin, anti-inflammatory drugs), or psychiatric illness/social situations that would limit compliance with study requirements.
- 2.2.5 Pregnant women are excluded from this study due to the potential for teratogenic effects. Because there is an unknown but potential risk for adverse events in nursing infants secondary to treatment of the mother with these agents, breastfeeding should be discontinued if the mother is being treated and not resumed until 28 days after completing therapy.
- 2.2.6 HIV-positive patients on combination antiretroviral therapy are ineligible because of the potential for pharmacokinetic interactions with these agents. In addition, these patients are at increased risk of lethal infections when treated with marrow-suppressive therapy.

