3. TREATMENT PLAN

Treatment will be administered primarily on an outpatient basis, although may be given inpatient based on location or status of patient. Reported adverse events and potential risks are described in Section 7. Appropriate dose modifications are described in Section 6. No investigational or commercial agents or therapies other than those described below may be administered with the intent to treat the patient's malignancy.

Each cycle will begin with ANC >1000 and platelet count >100 without transfusion support. At the beginning of each cycle pregnancy testing must be confirmed negative for females of child bearing potential and counseling regarding pregnancy risks must be confirmed for all patients

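### The bar on pro-thrombotic agents applies at entry only, while the contraception rule accepts birth control pills of any type throughout the study

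*Protocol*

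**What the plan says.** Protocol 2.1.3, among the restrictions on prior and current therapy, states: "Must not be receiving pro-thrombotic agents". It gives no definition, drug list or exception.

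Protocol 3.1.7, in the same run of eligibility items despite its number, asks women of child-bearing potential either to abstain or to use two methods, one of them highly effective. The highly effective methods include "IUD, birth control pills, injections, implants, tubal ligation" and a partner's vasectomy. Pills are not limited by hormone content. The duty runs "for the duration of study participation and at least 28 days after completion". The reason given is partly "because agents used in this trial are known to be teratogenic".

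Protocol 2.2.4 adds exclusions that bear on clotting: "history of thromboembolism unrelated to central line, patients with known predisposition syndrome for thromboembolism, patients receiving anticoagulation therapy", and also "patients receiving antiplatelet agents (aspirin, anti-inflammatory drugs". It does not mention hormonal contraception.

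For the treatment period, Protocol section 3 states: "No investigational or commercial agents or therapies other than those described below may be administered with the intent to treat" the malignancy. The calendar in section 6 has concurrent medications recorded, and its notes cover pregnancy testing but not the type of contraceptive.

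**The concern.** The exclusions in 2.1.3 and 2.2.4 show that the sponsor wanted patients to enter without an added thrombotic risk. The same exclusions mean that patients enter without anticoagulant or antiplatelet drugs. The contraception rule then sends some of them to a list on which an unqualified pill is an accepted choice.

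What is at stake is patient safety on a small scale. A site that follows the text exactly could start a combined pill in a patient taking lenalidomide and vorinostat, and so bring in the kind of agent that 2.1.3 keeps out at entry.

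**Working it through.** No arithmetic applies. The plan states no figure on this point, and the point depends on no sample size, error rate or effect size. The check sets the items side by side at two times.

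**Assumption.** Estrogen-containing contraceptives count as pro-thrombotic agents. The documents neither say this nor define the term. If the assumption is false, the concern falls away.

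**Who can be affected.** The age range is 1 to under 21 years, and the calendar schedules pregnancy tests, so the protocol expects some females of child-bearing potential. Those who abstain need no method.

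**At screening.**
- 2.1.3: a combined-pill user is receiving a pro-thrombotic agent and does not qualify.
- 3.1.7: the same patient has an accepted highly effective method.
- Eligibility items apply together, so she is ineligible unless she changes method. Abstinence, an IUD, tubal ligation, a partner's vasectomy or an estrogen-free hormonal method could satisfy both items. There is no contradiction, although the undefined term leaves each site to work this out.

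**After enrollment.**
- 2.1.3 is an eligibility item and has been met. It does not say that it continues during therapy.
- 3.1.7 does continue, through the study and for at least 28 days afterwards. A patient who was not using contraception at screening may start a method because of it, and pills are on the list.
- 2.2.4 is an entry exclusion and does not mention contraceptives.
- Section 3 restricts agents given against the tumor. A contraceptive is not such an agent.
- The calendar would record a new pill but does not bar it.

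**A comparison within the protocol.** Current anticancer therapy is barred at entry by 2.1.3 and barred again during treatment by section 3. Pro-thrombotic agents are barred at entry, with no matching rule during treatment in the available text. Where the protocol carries an entry restriction into treatment, it says so.

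**Result.** At screening the text gives an answer, on the stated assumption. After enrollment it leaves a combined pill open to a patient who must use a highly effective method.

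**The case against.** The strongest case on the other side has four parts.

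1. *The items do not conflict.* 3.1.7 sets a standard of contraceptive efficacy; it does not say that every listed product is otherwise permitted. A reader might infer that the protocol contradicts itself, by both accepting and barring the combined-pill user. The documents do not support that reading, because 2.1.3 decides the matter at entry and other methods remain. This part stands in full for screening. It does not reach a pill started later.

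2. *The premises come from outside.* No section calls estrogen contraceptives pro-thrombotic, and none states how far lenalidomide raises thrombotic risk. This stands. The first is an assumption. On the second, 2.1.3 and 2.2.4 show a concern about thrombosis but give no size, so none is claimed here.

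3. *The text is incomplete.* Section 3 points to sections on risks and dose modification that are not in the available text under those numbers, and a rule on concomitant drugs might sit there. This stands as a limit: the point is confined to the available text.

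4. *The silence is general.* The available text also has no explicit rule against starting anticoagulants, antiplatelet agents or enzyme-inducing anticonvulsants on study. That is true. Pills differ in that 3.1.7 itself requires a method and names pills as one that qualifies.

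**Conclusion.** The point holds in a limited form and is worth the sponsor's consideration. On the assumption that estrogen-containing contraceptives are pro-thrombotic, the available text permits a patient to start a combined pill during protocol therapy in order to comply with 3.1.7, contrary to the aim of 2.1.3 and 2.2.4.

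The size cannot be estimated. About 20 patients are planned, and the documents give no sex split, age distribution or contraceptive use. The number affected may be zero. The text does not say whether any listed injection or implant contains estrogen, so the finding itself concerns pills.

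A reader might also infer that thrombotic events from this source would distort the count of dose-limiting toxicities or the escalation. The documents offer no basis for that, and no effect on dose-limiting toxicities, escalation or analysis is claimed.

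**What to change.** Three changes of wording:

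- In 2.1.3, after the words on pro-thrombotic agents, add *(including estrogen-containing contraceptives)*, and state that the bar lasts for the whole of protocol therapy.
- In 3.1.7, qualify the list so that pills and any other hormonal method must be estrogen-free and still highly effective. The efficacy condition matters because 3.1.7 calls the study agents teratogenic.
- Confirm the method at counseling. The protocol already provides for this: "Females of childbearing potential must agree to ongoing pregnancy testing and counseling every 28 days about pregnancy precautions".

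No visit or test is added. The cost falls on a patient who prefers a combined pill: she must use another listed method or abstain. An IUD, tubal ligation, a partner's vasectomy and estrogen-free hormonal methods that meet the efficacy condition remain open. If a section outside the available text already restricts estrogen during therapy, a cross-reference in 3.1.7 would be enough.

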2.1.5 Karnofsky or Lansky performance status $\geq 50\%$

2.1.6 Life expectancy of greater than 8 weeks

2.1.7 Patients must have normal organ and marrow function as defined below:

Absolute neutrophil count	$\geq 1,000/\text{mcL}$
Platelets	$\geq 100,000/\text{mcL}$
Pulse oximetry	$> 93\%$
Total bilirubin	$\leq 1.5 \times$ upper limit of normal (ULN)
AST(SGOT)/ALT(SGPT)	$\leq 2.5 \times$ institutional upper limit of normal
Creatinine	within normal institutional limits OR
Creatinine clearance	$\geq 60 \text{ mL/min/1.73 m}^2$ for patients with creatinine levels above institutional normal.

3.1.7 Pregnancy and breast feeding

The effects of vorinostat and lenalidomide on the developing human fetus are unknown. For this reason and because agents used in this trial are known to be teratogenic, women of child-bearing potential must commit to complete abstinence or use TWO methods of birth control (one highly effective (i.e. IUD, birth control pills, injections, implants, tubal ligation, partner's vasectomy), and one additional method (i.e. male condom, diaphragm, cervical cap) for the duration of study participation and at least 28 days after completion. Females of childbearing potential must agree to ongoing pregnancy testing and counseling every 28 days about pregnancy precautions. If a female has not had a menstrual period in the preceding 24 consecutive months or has had a hysterectomy, the two methods of birth control requirement does not apply. Should a woman become pregnant or suspect she is pregnant while she or her partner is participating in this study, she should inform her treating physician immediately. Men treated or enrolled on this protocol must agree to use condoms for the duration of study participation, and 28 days after completion.

3.1.8 Patient or guardian ability to understand and provide written informed consent.

3.1.9 Must be able to swallow lenalidomide capsules.

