
A: Dose as assigned; administration schedule
 
B: Dose as assigned; administration schedule
 
a: Albumin, alkaline phosphatase, total bilirubin, bicarbonate, BUN, calcium, chloride, creatinine, glucose, LDH, phosphorus, potassium, total protein, SGOT [AST], SGPT [ALT], sodium.
 
b: Serum or urine pregnancy test (women of childbearing potential). Obtain 10-14 days prior to study enrollment and again within 24 hours prior to Day 1 of each cycle. Obtain weekly during cycle 1. Females with irregular menstruation must have a pregnancy test every 14 days while receiving protocol therapy (including breaks in treatment). Pregnancy test is also required if patient misses her period or has unusual menstrual bleeding. Pregnancy testing must also occur at Day 28 (and at Day 14 if female has irregular menstruation) after lenalidomide discontinuation).
 
c: Continue pattern of measurements while on study.
 
d: Off-study evaluation
 
e: As indicated based on diagnosis and tumor location.

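### Section 3.1.7 lifts two-method contraception after 24 months without menses whatever the cause, which does not establish infertility in pretreated patients under 21

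*Protocol*

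**What the plan says.** Section 3.1.7 of the Protocol (printed with that number among the section 2.1 inclusion criteria) sets the contraception rule. Its reason is stated: "because agents used in this trial are known to be teratogenic". Females of childbearing potential must either abstain completely or use one highly effective method plus one additional method, during the study and for at least 28 days afterwards.

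The exemption follows. It covers a female who "has not had a menstrual period in the preceding 24 consecutive months or has had a hysterectomy". The consequence, given in the same sentence, is that "the two methods of birth control requirement does not apply" to her. Nothing in the sentence refers to the cause of the amenorrhea, age, menarche or ovarian function.

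The population is defined in section 2.1. Item 2.1.4 gives the age range as "≥ 1 Age (in years) < 21". Item 2.1.1 says that the "patient must have received prior standard therapy in order to be considered eligible". Item 2.1.3 sets washout intervals for chemotherapy, nitrosourea, transplant, and focal and craniospinal radiation.

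Pregnancy testing is in section 3 and in footnote b of the Study Calendar (section 6). Footnote b requires a test before enrollment, weekly in cycle 1, and "again within 24 hours prior to Day 1 of each cycle". It adds two rules tied to menstrual history: "Females with irregular menstruation must have a pregnancy test every 14 days while receiving protocol therapy", and "Pregnancy test is also required if patient misses her period or has unusual menstrual bleeding".

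**The concern.** The rule gives 24 months without menses the same standing as a hysterectomy. A hysterectomy rules out pregnancy at any age. Absence of menses is reasonable evidence of lost fertility when natural menopause is the likely explanation, but this trial enrolls children, adolescents and adults under 21 who have already been treated for a central nervous system tumor.

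The stake is patient safety. A site that follows 3.1.7 literally may tell a post-menarchal adolescent with therapy-related or tumor-related amenorrhea that two-method contraception is not required of her while she takes agents the protocol itself treats as teratogenic.

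**Working it through.** The plan gives no figure on this point, so the check is a reading of the text plus one subtraction.

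1. **Age bound.** Inputs: upper age limit 21 (2.1.4) and waiver period 24 months (3.1.7). Latest possible age at last period for a post-menarchal female exempt at entry: 21 − 24/12 = 21 − 2 = 19. She was therefore under 19 at her last period, and natural menopause is not the expected reason.

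2. **Foreseeable routes to the waiver.** Prior standard therapy is mandatory (2.1.1), and 2.1.3 anticipates cytotoxic treatment, transplant and craniospinal radiation. Optic pathway tumors are named among eligible diagnoses. Contraceptive use is a third route. That these can suppress menses without ending fertility is general clinical knowledge. The items in 2.1.3 are washout intervals and say nothing about gonadal effect.

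3. **Who is released, reading 3.1.7 literally.**

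| Patient | Two-method rule | Infertility established? |
|---|---|---|
| Hysterectomy | lifted | yes |
| Post-menarchal, no menses for 24 months or more after therapy or from tumor | lifted | no |
| No menses for 24 months or more while on a contraceptive | lifted | no; she may still be using one method, but the text drops the second and the obligation to continue the first |
| Amenorrhea for less than 24 months | stays | not applicable |

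4. **Search for a qualifier elsewhere.** Sections 2.1 and 2.2, the Treatment Plan, and the Study Calendar with its footnotes neither narrow the 24-month condition nor define childbearing potential.

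5. **What remains for a released patient.** The waiver sentence names only the two-method requirement. Section 3 still asks for a negative test at each cycle start in females of childbearing potential, and for pregnancy-risk counseling to be confirmed for every patient. Footnote b's testing also stays. These controls detect a pregnancy, and the pre-cycle test keeps a detected pregnancy out of the next cycle, but neither prevents conception. The missed-period trigger in footnote b cannot work in a patient who has no periods. Section 3.1.7 does not say whether abstinence or a single method is still expected of her.

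**The case against.** The strongest case against the point has four parts.

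- **The harm rests on a clinical premise outside the documents.** No section mentions therapy-induced amenorrhea or return of fertility. This stands, so the premise is stated here as an assumption. The gap in the wording does not depend on it: the sentence asks for no evidence of infertility.
- **The affected group is very narrow.** A patient must be female, post-menarchal, without menses for two years, still fertile, at risk of pregnancy and not using contraception anyway, in a trial of at most 20 patients of both sexes (SAP 1.1). This stands, and it limits the weight of the point.
- **Safeguards remain, and the condition may lapse.** Testing and counseling continue. Because the condition looks at the preceding 24 months, the two-method rule arguably resumes if bleeding returns. This stands in part: conception before the first returning period would escape it. Nor does footnote b contradict the waiver, since extra testing for irregular menses and a waiver for prolonged absence are different controls.
- **A definition of childbearing potential may sit in text not supplied.** This cannot be excluded, although 3.1.7 refers to none.

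A reader might go further and infer that the waiver also removes pregnancy testing, by treating the 24-month condition as the definition of non-childbearing potential. The documents do not say so; the sentence lifts only the two-method rule.

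**Conclusion.** The point holds as a defect in a stated safety rule: 3.1.7 accepts 24 months of amenorrhea from any cause as sufficient to drop two-method contraception, in a pretreated population under 21 where therapy, tumor or contraceptives are likelier causes than natural menopause. It should be corrected. Confidence is medium, because the conclusion assumes that such amenorrhea need not mean infertility and that no section outside the supplied text narrows the rule.

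No size is claimed. The number affected cannot be derived from the documents and may be zero. A reader might take the dosing days between scheduled tests as a measure of the harm: from cycle 2, cycle-start tests 28 days apart span 21 lenalidomide days and 14 vorinostat days, taking the schema as daily dosing. Those counts are the same for every female tested at cycle start, exempt or not. They describe the testing schedule and show no increment due to the waiver.

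**What to change.** Replace the exemption sentence in 3.1.7 with: *The two-method requirement does not apply to females who have had a hysterectomy or have documented permanent infertility (e.g., bilateral oophorectomy), or who are prepubertal; amenorrhea due to prior therapy, tumor or contraceptive use does not by itself qualify.*

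Leave the pregnancy testing and counseling in sections 3, 3.1.7 and 6 unchanged.

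The cost is small. One sentence changes, with no new visit and no effect on sample size or analysis. Sites need documentation where permanent infertility is claimed. A few more patients come under the contraception rule, which complete abstinence also satisfies. Because 2.1.3 bars pro-thrombotic agents while 3.1.7 lists birth control pills as an acceptable method, the choice of method may need thought for those patients. Whether a given pill counts as pro-thrombotic is not stated, and 3.1.7 lists other methods, such as an IUD.
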